9.5.2. Exact confidence intervals (CIs)

The exact confidence interval within a group for an incidence rate (per 100 person-years):

To estimate the confidence limit of the incidence rate, the exact Poisson confidence limit will be used [[Clopper, 1934](#)]:

If n is the number of subjects presenting a given characteristic among these Ny subjects per year, the true incidence rate can be estimated by $(n/Ny)*100$. Its exact $(1-\alpha)\%$ confidence interval is obtained from:

$CINV(\alpha/2, 2*n)/2/Ny*100$ as the lower boundary

and

$CINV((1-\alpha/2), 2*(n+1))/2/Ny*100$ as the upper boundary.

where $CINV(probability, degrees\ of\ freedom)$ returns the inverse of the chi-squared probability distribution and α is the type I error rate.

9.5.3. Computation of proportion affected

Proportion affected will be computed as the number of subject who had at least one episode in the age interval divided by the total number of subjects at start of considered age strata. A 95% CI will be computed using an exact method for a Poisson variable.

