5.2. Analysis of primary objectives

The primary objectives analyses will be performed on the PPSs overall and possibly by region or other relevant grouping (the groupings are specific to each analysis). *If there is a difference of 5% or more between the number of participants in the enrolled set and the PPS, primary objectives analyses on the enrolled set will also be performed.*

5.2.1. To determine the frequency of pregnancy outcomes in healthy pregnant women with uncomplicated pregnancies at time of enrollment.

5.2.1.1. Analysis of pregnancy outcomes planned in the protocol.

The number and percentage (with exact 95% CI) of women presenting the following outcomes: live birth, fetal death/stillbirth (antepartum or intrapartum), and elective/therapeutic termination will be reported for each event by presence or absence of congenital anomalies.

5.2.1.2. Additional considerations:

The following analysis will be done on the maternal PPS. The intervals of interest are Visit 1 to Visit 5 (delivery). Details of exact confidence intervals analysis are described in section 9.5.2. All frequencies will be reported overall, by country, and if applicable, by region. For example, if there are few subjects for the events of interest, tables by region will also be presented. Frequencies of pregnancy related events of interest will also be presented by age strata (18-34, 35-39, ≥ 40 years).

The number and percentage (with exact 95% CI) of women presenting the following outcomes will be reported:

- Live birth with no congenital anomalies,
- Live birth with congenital anomalies,
- Fetal death/stillbirth (loss at or after 22 weeks of gestation) with no congenital anomalies,
 - Antepartum stillbirth
 - Intrapartum stillbirth

- Fetal death/still birth (loss at or after 22 weeks of gestation) with congenital anomalies,
 - Antepartum stillbirth
 - Intrapartum stillbirth
- Elective/therapeutic termination with no congenital anomalies,
- Elective/therapeutic termination with congenital anomalies

5.2.2. To determine the frequencies of pregnancy related events of interest in healthy pregnant women with uncomplicated pregnancies from visit 1 through visit 6.

Although pregnancy related events of interest occur within the first 42 days after delivery they may only be detected later, and are to be reported throughout the study

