5.3.6.2. Additional considerations

A correction from the analysis planned in protocol in section 5.3.6.1 is that we will be reporting on all cause LRTIs and RSV associated LRTIs.

This analysis will be based on the infant PPS and will be done on the first episode of all, of severe, and of very severe RSV LRTIs (Section 2.2).

Incidence analyses will be performed overall, by country and by age strata (0-2 months, 0-5 months, and 0-11 months). If applicable (in the case of low numbers of incidence), incidence analyses will also be presented by region (Section 9.3). Incidence rates will also be calculated in one-month intervals from birth to one year of age, please see the monthly infant age intervals in Section 9.3.

The analysis of RSV disease incidence is summarized in the table below showing endpoints and analytic methods, these include incidence rate, proportion affected, and incidence proportion.

Incidence rate is the number of first events per person time. Incidence proportion is the number of first RSV LRTI over population at risk during the specified time period (0-2 months, 0-5 months and 0-11 months). Proportion affected is the number of subjects with at least one episode of RSV LRTI at age interval over the total number of subjects at the start of the age interval.

For each of the RSV LRTI endpoints listed in [Table 11](#), the 95% CI will be computed as described in section [9.5.2](#). Kaplan-Meier curves presenting the cumulative probability of the first episode will be displayed overall. The cumulative probability of presenting the first episode will be given with its 95% CI at the end of the follow-up.

Frequencies of repeat occurrences of RSV LRTI, severe LRTI and very severe LRTI will be tabulated.

Cumulative incidence will be presented from birth to one year of life by monthly intervals (Subgroups in section [9.3](#)).

Table 6 Summary of RSV incidence analyses for RSV LRTI of infants from birth to 1 year (Visit 1-NB to visit 4-NB)

Endpoints	Incidence analysis method	Subgroup
All RSV LRTI Severe RSV LRTI Very Severe RSV LRTI	Incidence rates of first episode Cumulative probability of first episode (Kaplan Meier)	Overall, by country, and by age strata
All RSV LRTI Severe RSV LRTI Very Severe RSV LRTI	Proportion affected by all new episodes	Overall, by country, and by age strata
All RSV LRTI Severe RSV LRTI Very Severe RSV LRTI	Incidence proportion of first episode	Overall and by country within each age strata)

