9. NON-STANDARD DATA DERIVATION RULES AND STATISTICAL METHODS

9.1. Data Derivation

9.1.1. Maternal blood and cord blood

Antibody titres will be obtained from maternal blood and cord blood at delivery. The GMT/GMC and its 95% CI will be obtained by exponentiating the mean and its 95% CI of the log-transformed titres/concentrations. All CI computed will be two-sided 95% CI.

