10.1.5. Statistical methodology

10.1.5.1. Exact confidence intervals around proportions

The exact confidence intervals around within-group proportions are derived using the method of Clopper and Pearson [[Clopper, 1934](#)].

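### SAP 9.5.3 orders a Poisson interval for proportion affected, a binomial proportion, and the percentages in 5.2, 5.3.2.2 and 5.3.6.2 point to a rate-only CI section, both in conflict with the Clopper-Pearson rule in 10.1.5.1

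*SAP*

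**What the plan says.** All references are to the current text of the SAP (Amendment 2).

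- **Section 9.5.3** defines proportion affected in these terms: "the number of subject who had at least one episode in the age interval divided by the total number of subjects at start of considered" (the closing words refer to the age stratum). It goes on to say: "A 95% CI will be computed using an exact method for a Poisson variable".
- **Section 9.5.2** is the only section that the objective-level text cites for exact intervals. It is limited to incidence rates per 100 person-years: "To estimate the confidence limit of the incidence rate, the exact Poisson confidence limit will be used". Its limits are chi-square quantiles divided by a person-time denominator, Ny. It contains no binomial formula.
- **Section 5.2.1.2** (pregnancy outcomes) says: "Details of exact confidence intervals analysis are described in section 9.5.2". Sections 5.2.2.2 (pregnancy related events), 5.2.3.2 (neonatal events) and 5.3.2.2 (pregnancy related events by GAIA level) carry the same pointer.
- **Section 5.3.6.2** says of the RSV-LRTI endpoints: "the 95% CI will be computed as described in section"; the section it names is 9.5.2. Those endpoints include proportion affected and incidence proportion as well as the incidence rate.
- **Section 9.5.4** (incidence proportion) asks for an exact method without naming one.
- **Annex 10.1.5.1** says: "The exact confidence intervals around within-group proportions are derived using the method of Clopper and Pearson".
- **The opening of section 5 and section 10.1** both bring the rules of 10.1 into force together with those of section 9. Neither says which prevails if they differ.

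**The concern.** Proportion affected cannot exceed 1 and its denominator is a number of infants, not person-time. A Poisson interval leaves out the factor 1 − p in the binomial variance, so it is too wide by an amount that grows with p, and nothing keeps its upper limit at or below 100%. For this quantity the study-specific text and the annex name different methods.

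The primary percentages have the same difficulty one step removed. Their sections send the programmer to a formula that needs person-years, which those analyses do not have. The programmer must either put the number of subjects in place of Ny, which gives Poisson limits, or disregard the pointer and find 10.1.5.1. Two programmers could reasonably produce different tables.

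The study exists to supply background frequencies for later maternal immunization trials, and the intervals are part of what it delivers.

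**Working it through.** The SAP states no interval or expected proportion to reproduce, so the check compares the two methods over a range of assumed proportions.

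**Inputs**
- Two-sided 95% level, α = 0.05 (9.1.1: "All CI computed will be two-sided 95% CI").
- N of about 2300 overall (2.1) and about 200 to 300 per country (note to Table 2); 250 is used for one country.
- Event proportions from 1% to 99%: assumed.

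**Formulas**, for n subjects with the event out of N
- Section 9.5.2 with N in place of Ny: lower = χ²(0.025; 2n)/(2N), upper = χ²(0.975; 2(n+1))/(2N).
- Clopper-Pearson: lower = Beta(0.025; n, N−n+1), upper = Beta(0.975; n+1, N−n).

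**Expected size.** The count has variance Np under Poisson and Np(1−p) under the binomial, so the ratio of widths should be close to 1/√(1−p). This gives 1/√0.9 = 1.05 at 10%, 1/√0.8 = 1.12 at 20%, 1/√0.7 = 1.20 at 30% and 1/√0.03 = 5.8 at 97%.

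**Exact results**

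| n/N | p | Poisson, % | Clopper-Pearson, % | Width ratio |
|---|---|---|---|---|
| 23/2300 | 1% | 0.63 to 1.50 | 0.63 to 1.50 | 1.01 |
| 230/2300 | 10% | 8.75 to 11.38 | 8.80 to 11.30 | 1.05 |
| 460/2300 | 20% | 18.21 to 21.91 | 18.38 to 21.69 | 1.12 |
| 690/2300 | 30% | 27.80 to 32.32 | 28.13 to 31.92 | 1.19 |
| 1150/2300 | 50% | 47.15 to 52.98 | 47.94 to 52.06 | 1.41 |
| 2070/2300 | 90% | 86.16 to 93.96 | 88.70 to 91.20 | 3.1 |
| 2231/2300 | 97% | 93.02 to 101.11 | 96.22 to 97.66 | 5.6 |
| 2277/2300 | 99% | 94.98 to 103.15 | 98.50 to 99.37 | 9.5 |
| 25/250 | 10% | 6.47 to 14.76 | 6.58 to 14.41 | 1.06 |
| 50/250 | 20% | 14.84 to 26.37 | 15.22 to 25.50 | 1.12 |
| 243/250 | 97.2% | 85.4 to 110.2 | 94.3 to 98.9 | 5.5 |

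**Thresholds.** The width doubles only from a proportion of about 75% and triples only from about 90%. The Poisson upper limit first reaches 100% at 219/250 (87.6%) for one country and at 2206/2300 (95.9%) overall.

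**Where the large effect can occur.** Among the outcomes whose interval is sent to 9.5.2, the one that would in practice lie near 100% is live birth with no congenital anomalies. Uncommon pregnancy and neonatal events sit in the top rows, where the two methods almost coincide. Proportion affected by RSV-LRTI would need an attack rate of about 75% before the interval even doubled in width.

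**The case against.** The strongest defence is that the SAP already contains the right rule. Section 5 opens by placing statistical methods in sections 9 and 10.1, section 10.1 repeats that its rules apply along with those of section 9, and 10.1.5.1 is the only rule addressed to within-group proportions in general. Section 9.5.2 confines itself to rates per person-time, so on its own terms it does not cover pregnancy outcomes or neonatal events. For the primary percentages this objection stands. A reader might infer that the SAP prescribes Poisson limits for them, but the text does not go that far: the pointer is wrong and conflicts with the annex. The objection does not reach 9.5.3, where the study-specific sentence names Poisson outright for a proportion.

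A reader might also infer that intervals several times too wide, passing 100%, are a general feature of these analyses. The figures do not support that. At proportions of 20% or less the excess width is at most about 12%.

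Nor do the symptom frequencies in 5.3.7.2 and 5.4.1.2 belong here, because no confidence interval is planned for them.

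Finally, where the two intervals differ appreciably, the Poisson one is the wider, so the error is conservative. Section 6 describes the analyses as descriptive, and no decision threshold is tied to these limits. That lowers the priority but does not make the instruction correct.

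**Conclusion.** The point holds in two parts. Section 9.5.3 names the wrong interval for proportion affected and contradicts 10.1.5.1. Sections 5.2.1.2, 5.2.2.2, 5.2.3.2 and 5.3.2.2, and 5.3.6.2 for its proportions, refer to a section that cannot supply an interval for a proportion; this is a misdirected reference in conflict with the annex.

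The consequence is small for low proportions and large only near 100%. For live birth with no congenital anomalies, followed literally, the interval would be roughly 3 to 9.5 times too wide if the true frequency lies between 90% and 99% of 2300. The overall upper limit would pass 100% from about 96%, and a country's limit would do so earlier. These sizes rest on assumed proportions and on N being put in place of Ny. The matter should be fixed before the tables are programmed, but it is not critical, since no point estimate changes.

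**What to change.** - **9.5.3:** replace the Poisson method with the Clopper-Pearson method and cite 10.1.5.1.
- **5.2.1.2, 5.2.2.2, 5.2.3.2 and 5.3.2.2:** change the reference for the exact interval from 9.5.2 to 10.1.5.1.
- **5.3.6.2:** refer proportion affected and incidence proportion to 10.1.5.1, and leave the incidence rate with 9.5.2.
- **9.5.2:** keep it for person-time rates only.

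Naming Clopper-Pearson in 9.5.4 as well would be tidy but is not essential, because an exact method for a proportion is already covered by 10.1.5.1.

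The cost is a few words in the SAP and a small programming change. No data collection is affected.

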9.5.4. Computation of incidence proportion

Incidence proportion will be computed as the number of subjects who had at least one episode in the age interval (monthly) divided by the number of subject at risk of event at the beginning of the age interval. A subject that has an event will no longer consider of at risk, i.e. subjects with event in 0 – 1 month are excluded from denominator for future monthly incidence calculation. A 95% CI will be computed using an exact method.

9.5.5. Cox models

All multivariable modelling will be done in a stepwise manner using backward elimination and statistical significance.

9.5.5.1. Univariate Models

Please see section [5.4.4.2](#). Univariate modelling will be done to first determine which risk factors are associated with which event of interest.

For each potential risk factor:

- Frequency tables will be generated as appropriate, for categorical variables.
- Mean, median, standard error, minimum, maximum and number of missing values will be provided as appropriate, for continuous data.

For pairwise distributions:

- Cross-tabulations (i.e. two-way frequency tables) will be generated as appropriate, for categorical-categorical pairs;
- Mean, median, standard error, minimum, maximum and number of missing values by category will be provided as appropriate, for continuous-categorical pairs;

9.5.5.2. Multivariable Models

Covariate selection will be done using statistical significance: the final multivariable regression models will include all potential risk factors with a simple regression model with p-value < 0.10. The number of covariates included in the models will depend on the number of events (at least 10 events per covariate). The models will be performed only if the number of events is sufficient (at least 10 events per covariate). In addition, depending on the data and the validity of the model assumptions, other models could be explored or the models could be simplified.

The results from the multivariable regression models will include hazard ratios (Cox regression models) and odds ratios (logistic and longitudinal logistic regression models) and their 95% CI.

9.5.5.3. Multiple Logistic Regression models

Multiple logistic regression models will be used to test the association between events of interest and risk factors. PROC LOGISTIC or PROC GENMOD can be used. What is tested will depend on how many people are observed with these outcome and risk factors and if they are associated in the univariate analysis.

9.5.6. Multiple Poisson/negative binomial models

PROC GENMOD can be used for multiple Poisson/negative binomial modelling.

10. ANNEXES**10.1. Business rules for standard data derivations and statistical methods**

This section contains GSK Vaccines' standard rules for data display and derivation for clinical and epidemiological studies. These rules will be applied along with those detailed in section 9 (additional study-specific rules).

10.1.1. Age

Age of infant will be expressed in months and will be computed as the number of complete calendar months between the date of birth (DOB) and the date of event. For example:

DOB = 10JUN2017, Date of event = 09JUL2018 -> Age = 12 months

DOB = 10JUN2017, Date of event = 10JUL2018 -> Age = 13 months

Age of the mother at the time of childbirth will be expressed in years and will be computed as the number of complete calendar years between the birth date of the infant and the birth date of the mother. For example:

DOB = 10SEP1983, Date of vaccination = 09SEP2018 -> Age = 34 years

DOB = 10SEP1983, Date of vaccination = 10SEP2018 -> Age = 35 years

10.1.2. Handling of missing data**10.1.2.1. Dates**

When partially completed dates (i.e. with missing day or month) are used in calculations, the following standard rules will be applied:

- A missing day will be replaced by 15
- A missing day and month will be replaced by June 30th.

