9.5. Statistical Methods

9.5.1. Computation of incidence rates

For each endpoint, the incidence rate (IR, number of episodes/endpoints per 100 person-years) will be calculated by dividing the number of subjects reporting the first episode over the follow-up period by the total person-year. A 95% CI will be computed using an exact method for a Poisson variable as described below.

The person-time at risk for an event of interest (RSV-LRTI or RSV hospitalization) will be calculated as the time between the date of birth and the end of the at-risk period or the earliest of the followings:

- Date of first diagnosis of event of interest (e.g. first episode of RSV-LRTI);
- Date when child reaches 1 year (or 6 months if analysis is done during the interim analysis);
- Date of death;
- Date of last follow-up in study.

Please note that in a case where a subject comes to an assessment visits, has LRTI symptoms, is not confirmed for RSV infection via a nasal swab (because either no nasal swab was taken or the lab yielded invalid results), then we will consider the subject as not have a laboratory-confirmed event. The Subject will therefore be censored at the event ($n=0$, $T=$ from start of the follow-up period at risk up to event).

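### The partial-date rule (day 15, June 30) has no bounds and can place an infant event before birth or after the first birthday

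*SAP*

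**What the plan says.** Section 10.1.2.1 of the current SAP (Amendment 2) states its scope as follows: "When partially completed dates (i.e. with missing day or month) are used in calculations, the following standard rules will be applied". Two rules follow: "A missing day will be replaced by 15" and "A missing day and month will be replaced by June 30th". No lower or upper limit is attached to either. The same two rules stand in the first version of the SAP and in Amendment 1.

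The opening of Section 10.1 makes the annex operative in this study: "These rules will be applied along with those detailed in section 9 (additional study-specific rules"). Section 9 contains no date rule that replaces or limits it.

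The infant analyses are anchored to birth. In Section 9.5.1, time at risk is "calculated as the time between the date of birth and the end of the at-risk period" or the earliest of several dates, one of which is "Date when child reaches 1 year (or 6 months if analysis is done during the interim analysis"). In Section 10.1.1, infant age is "computed as the number of complete calendar months between the date of birth (DOB) and the date of event". Section 5.3.6.2 then reports incidence in strata of 0-2, 0-5 and 0-11 months and in one-month intervals.

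**The concern.** A constant calendar date takes no account of when the infant was born. With day and month missing, an infant born after June 30 with an event in the birth year is given an event before birth. An infant born before June 30 with an event in the following calendar year is given one after the first birthday. With only the day missing, the same can happen within the birth month or the month of the first birthday.

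The SAP does not say what becomes of such a record. One programmer might drop it, another set the age to zero, and a third keep a negative age. At stake are the age-specific RSV-LRTI and RSV hospitalization results, where an event may be lost or counted in the wrong age interval. A single misplaced event matters most in sparse cells, such as very severe RSV-LRTI within one country or one month of age.

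**Working it through.** The SAP states no figure on this point, so there is none to reproduce.

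**Inputs from the SAP.** Day 15 and June 30 (10.1.2.1). Time at risk from birth to the first birthday at most (9.5.1). Age in completed calendar months (10.1.1). Neonatal events limited to the first 28 days (2.1). RSV seasons by site (9.1.5, Table 11).

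**Assumptions, because the SAP gives no distribution.** Births are uniform over the year, event age is uniform over 0 to 1 year, and the year of the event is known (also the month, where only the day is missing).

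**Examples.**
- Born 10 Oct 2019, event recorded as 2019: imputed 30 Jun 2019, 102 days before birth.
- Born 10 Mar 2019, event recorded as 2020: imputed 30 Jun 2020, 112 days after the first birthday.
- Born 20 May 2019, event recorded as May 2019: imputed 15 May 2019, 5 days before birth.

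**Day and month missing, by formula.** Let u be the time of birth within the year and a the age at the event in years, both uniform on (0, 1). June 30 is close to 0.5.
- Before birth: the event is in the birth year (u + a < 1) and u > 0.5. The probability is the integral of (1 − u) from 0.5 to 1, which is 1/8.
- After the first birthday: the event is in the next year (u + a ≥ 1) and u < 0.5. The probability is the integral of u from 0 to 0.5, which is 1/8.
- Total: 1/8 + 1/8 = 25%.

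**Check by enumeration.** Taking all 365 birth dates of 2019 and every event day before the first birthday gives 12.75% before birth and 12.29% on or after the first birthday, 25.04% in total. The mean absolute shift is 91 days over all imputed dates and 81 days over those that stay in the window. Of the latter, 89% fall in the wrong month of age.

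**Sensitivity to the assumptions, day and month missing.**

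| Scenario | Out of window |
|---|---|
| Births in Q1 / Q2 / Q3 / Q4 | 12.3% / 37.2% / 37.8% / 12.7% |
| Events only May-July | 6.9% |
| Events only March-July | 14.1% |
| Events only June-October | 14.4% |
| Events only July-December | 25.3% |
| Events only September-April | 33.5% |
| Events at 0-180 days | 25.8% |
| Events at 0-90 days | 38.1% |
| Events at 0-28 days | 46.6% |

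The range is about 7% to 47%.

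**Only the day missing, same enumeration.** 1.14% fall before birth and 0.94% on or after the first birthday, 2.08% in total. For events at 0-90 days the total is 4.6%, and for events at 0-28 days 14.4%. The shift is never more than 16 days. Of the dates that stay in the window, 23% change month of age.

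**The case against.** The strongest reply is that few dates will be affected. Section 2.1 describes scripted active contacts at regular intervals, diary cards, and a clinic appointment within three days of symptom onset when wheezing or difficulty breathing is reported. Admission dates come from an inpatient form (9.4.5.1). At such contacts the month of onset will nearly always be known. Section 7 also requires cleaned data, which gives an opportunity to query partial dates, although Section 8 relaxes this for the Epoch 002 analysis. This reply stands: it limits the size of the effect, but it does not make the rule valid for the dates it reaches.

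A reader might infer three stronger things that the SAP does not support.

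- *That a quarter of infant event dates become impossible.* The 25% applies only to dates missing both day and month, and it rests on uniform timing, which sits poorly with the seasonal sites in Table 11. The likelier case, a missing day alone, gives about 2%.
- *That person-time is generally corrupted.* Section 9.5.1 ends person-time at the earliest of several dates including the first birthday, so a late imputed date cannot extend it. Negative person-time arises only if a partial symptom-onset date serves as the event date. Section 9.5.1 stops the clock at first diagnosis, while Section 9.4.2.1 defines episode start by symptom onset. If diagnosis means the recorded visit or swab, a partial onset date does not enter person-time.
- *That the primary results are affected.* Those are counts and percentages of subjects with events (Section 5.2), and no primary result has been shown to change. RSV incidence is a secondary objective.

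It can also be said that mid-period imputation is a sponsor standard in a generic annex. That is so, and the defaults themselves can stay. The fault is the absence of bounds.

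**Conclusion.** The point holds as a minor defect in a stated rule. Section 10.1.2.1 can return a date that contradicts the SAP's own definitions of infant age and time at risk, and nothing else in the SAP prevents it. The expected share is about 2% of dates missing only the day (about 14% at 0-28 days), and about 25% of dates missing day and month, with a range of about 7% to 47%. All these shares are conditional on a date being partial and depend on assumed birth and event distributions.

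The number of partial dates is not given and is probably small, so overall incidence should barely move. What remains is misplaced or dropped events in monthly and early-infancy cells with few events. The change is worth making because it is nearly free, not because the study's conclusions depend on it.

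**What to change.** Keep day 15 and June 30 as defaults in Section 10.1.2.1 and add a bound for infant event dates. The imputed date should be no earlier than the date of birth (or the end of the previous episode), and no later than the earliest of the episode's assessment visit, swab or admission date, death, last contact or first birthday. The visit, swab and admission limits are meant for onset dates; where the admission date is itself the partial one, only the remaining limits apply. If the recorded part of the date and the bounds share no day, the record should be queried rather than imputed.

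Out-of-window dates then fall to 0% by construction. The cost is one or two sentences in the SAP and a simple programming check, with no new data.
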